10.5 Secondary Objectives

Evaluate the efficacy of intensive antihypertensive control compared to conventional antihypertensive control in the prevention of clinically significant (CTCAE Grade 2 or higher) and radiologically extensive osteonecrosis, overall and stratified by joints.

A one-sided Chi-square test will be performed on a 2x2 contingency table similar to that in the primary objective, only now the columns are CTCAE Grade 2 ON (No/Yes). This analysis will also be performed for the knees and hips separately. MRI-defined extensive osteonecrosis will also be performed as described above, for knees and hip separately using Chi-square test on contingency tables.

Compare the frequency of clinically and radiographically significant osteonecrosis between patients receiving antihypertensive intervention and historical controls.

The historical control cohort consists of all patients enrolled on TOT-XV and TOT-XVI studies with age at diagnosis 10 years or older. The rate of clinically significant (CTCAE Grade 2+) ON and radiographically significant findings (number of affected joints) will be compared between the intensive BP treatment arm and the historical cohort by Chi-square tests.

Compare blood pressures achieved in intensive and conventional arms using both pressures obtained as part of routine patient care and ambulatory blood pressure monitoring.

The comparison will be done by regression modeling using mixed effect models to account for intra-patient repeated blood pressure measurements. The response variable is blood pressure, the explanatory variables include the BP control arm (intensive vs. conventional), age, sex, race and a random effect with AR(1) working covariance structure.

Compare levels of vascular dysfunction as measured physiologically, radiographically, and in blood samples in patients receiving intensive compared to standard antihypertensive therapy.

The levels of vascular dysfunction are measured by markers such as MRI, eNO synthetase, Von Willebrand Factor, TNF-alpha, D-dimer, PAI-1, E-selectin and ICAM-1; the measurements are all continuous. Each marker will be compared between the intensive BP treatment arm and the standard care arm by Wilcoxon rank-sum test.

Time frame: The analysis will begin within 6 months after the MRI assessments of the last randomized patient is completed.

Responsible investigators: [name], [name]

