5.5 Long-Term Follow-up Evaluations

Patients will be followed for the development of osteonecrosis as per the TOT17 protocol.

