7.0 OFF TREATMENT AND OFF STUDY CRITERIA

7.1 Off-Study Criteria

- Death
- Lost to follow-up
- Request of the patient/parent/LAR
- Completion/discontinuation of Total 17 therapy
- Discretion of the Study PI, such as the following
- The researcher decides that continuing in the study would be harmful, such as:
 - A treatment is needed that is not allowed on this study
 - The participant misses so many appointments that the data cannot be used in the study
 - The participant's condition gets worse
 - New information is learned that a better treatment is available, or that the study is not in the participant's best interest
 - Study evaluations are complete

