7.2 Off-Therapy Criteria

- Completion of prescribed therapy duration (completion of week 19 dexamethasone).
- Discontinuation of TOT17 therapy
- Treatment with high-risk arm therapy (i.e. chimeric antigen receptor T-cell therapy, Reintensification, or transplant)
- Development of unacceptable toxicity during treatment
- Refusal of therapy
- A research participant may also be taken off treatment or off of the study at the discretion of the study PI if persistent non-adherence with protocol directed therapy is documented.

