10.8 Summary of Primary and Secondary Objectives

Objective#	Objective Type	Analysis#	Resp Party	Stat	Safety	Analysis Measure	Analysis Title	Data Collection Time Frame	# of Participants
1.1.1	P	1	SEK	CC	N	Patient	Intensive vs. conventional hypertension control effect on osteonecrosis	Time on therapy	160
1.2.1	S	2	SEK	CC	N	Patient/ Joint	Antihypertensive intervention patients over time	Time on therapy/ Reinduction II	160
1.2.2	S	3	SCK/CM	CC	N	Patient/ Joint	Antihypertensive treated patients vs. historic control	Time on therapy/ Reinduction II	160
1.2.3	S	4	ND	CC	N	Patient	Blood pressure achieved by intervention arm	Through reinduction II	160
1.2.4	S	5	CM	CC	N	Patient	Induction MRI	Induction	80
1.2.4	S	6	DM	CC	N	Patient	Vascular function by vasomotor testing	Induction, consolidation, off therapy	80
1.2.4	S	7	SEK	CC	N	Patient	Blood markers of vascular dysfunction	Induction, reinduction II	160
1.3.1	E	7	SEK	CC	N	Patient	Blood markers of osteonecrosis risk	Induction, reinduction II	160
1.3.2	E	3/5	SCK/CM	CC	N	Patient	Early vs late MRI findings of osteonecrosis	Induction, Reinduction	80
1.3.3	E	8	ND	CC	N	Patient	ABPM blood pressures vs osteonecrosis	Induction	160
1.3.4	E	7	GB	CC	N	Patient	Echo changes at reinduction vs induction blood pressure	Reinduction II	80
1.3.5	E	9	EK	CC	N	Patient	HRQoL and symptom survey	Induction, reinduction II, week 49	160
1.3.5	E	10	EK	NA	N	Patient	Narrative symptom description	Week 49	80

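### Objective 1.2.2 compares crude Grade 2+ osteonecrosis proportions with TOT-XV/XVI without a common observation window, which favours intensive control if historical events are counted for longer

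*Combined protocol and SAP*

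**What the plan says.** Objective 1.2.2 sets the intensive arm against history. Section 10.5 defines the comparator: "The historical control cohort consists of all patients enrolled on TOT-XV and TOT-XVI studies with age at diagnosis 10 years or older". Clinically significant ON (CTCAE Grade 2+) and the number of affected joints "will be compared between the intensive BP treatment arm and the historical cohort by Chi-square tests". No sidedness, alpha or power is given for this comparison, and no event cut-off for either cohort. On timing, Section 10.5 says: "The analysis will begin within 6 months after the MRI assessments of the last randomized patient is completed".

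The nearest thing to a window is the data-collection entry for 1.2.2 in the Section 10.8 table: "Time on therapy/ Reinduction II". It is not expressed in months, and the table does not say whether it governs the historical cohort. Other sections bear on how long ON is observed in the trial:

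- Section 5.5: "Patients will be followed for the development of osteonecrosis as per the TOT17 protocol".
- Section 7.1 lists as an off-study reason: "Completion/discontinuation of Total 17 therapy".
- Section 9.1 says that Grade 2+ ON is recorded, without a duration, and separately limits adverse-event capture to 4 weeks after removal from treatment.

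**The concern.** A Chi-square test on yes/no proportions is fair only if both cohorts had the same time in which to have an event. Here the trial side has staggered follow-up. The MRI falls at about month 9 (Section 10.4), so the last patients may be analysed with 9-15 months of observation, while the first have several years. Section 2.1 says symptomatic cases often arise within two years of starting treatment, so some late-enrolled patients would be counted as event-free only because they have not been observed for long enough.

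Nothing requires TOT-XV/XVI events to be cut at a matching time. If they are counted for longer, the intensive arm looks better with no treatment effect. Section 2.1 shows that the counting window moves the historical rate: among normotensive patients ON falls from 38% to 34% when only on-therapy events count.

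Two further mismatches affect the same comparison. The historical cohort is selected on age alone, whereas the 140-patient chart review in Section 10.4 applied HYPERION eligibility. For the radiographic half, no MRI time point is stated for the historical patients.

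**Working it through.** **The plan's own figure.** None exists for 1.2.2. The nearest is the 78.7% power in Section 10.4. The control rate is 0.854 × 50/120 + 0.146 × 0.20 = 0.385. A one-sided Fisher exact test of 0.385 versus 0.20, with 80 per arm at 5%, has power 78.66%, so that figure reproduces. It concerns the randomised primary comparison, which this point does not touch.

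**Inputs from the documents**
- Intensive arm: 80 patients (Section 10.1).
- Accrual A: 180/60 per year = 36 months, up to 42 months (Section 10.1).
- Shortest follow-up g: 9 months (MRI) to 9 + 6 = 15 months (Sections 10.4, 10.5).
- Symptomatic ON rate: about 40% (Section 2.1).

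**Assumptions, not in the documents**
- No true effect, and all symptomatic events occur by month 24.
- Historical cohort of 235 (the Section 2.1 series), counted to month 24.
- Uniform accrual, with the data cut when analysis begins.
- A share f9 of events occurs by month 9; the rest are spread evenly to month 24.
- Two-sided 5% test; only results favouring intensive control are counted.

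**Step 1: short follow-up.** Share of patients under 24 months = (24 − g)/A.
- A = 36, g = 9: 15/36 = 41.7%.
- A = 42, g = 15: 9/42 = 21.4%.

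**Step 2: share of events missed.** Those patients miss on average (1 − f9)(24 − g)/(2 × 15) of events. Overall, missed = (1 − f9)(24 − g)²/(30A).

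**Step 3: apparent trial rate** = 40% × (1 − missed).

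**Step 4: false benefit.** Exact binomial enumeration of the uncorrected Chi-square test, 80 versus 235. With equal windows it gives 2.5%.

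| f9 | A=36, g=9: missed | apparent rate | false benefit | A=42, g=15: missed | apparent rate | false benefit |
|---|---|---|---|---|---|---|
| 0.50 | 10.4% | 35.8% | 9.5% | 3.2% | 38.7% | 3.9% |
| 0.60 | 8.3% | 36.7% | 7.5% | 2.6% | 39.0% | 3.6% |
| 0.75 | 5.2% | 37.9% | 5.1% | 1.6% | 39.4% | 3.1% |
| 0.90 | 2.1% | 39.2% | 3.3% | 0.6% | 39.7% | 2.7% |

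These two columns bracket the accrual and timing range. At a one-sided 5% level, which Section 10.5 does not exclude for 1.2.2, f9 of 0.50-0.75 gives 6.2-16.4% against 5.1%.

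**Step 5: a check that needs no onset model.** Section 2.1 gives 94 hypertensive patients of 235, hence 141 normotensive. Assuming the same denominators in both windows:
- Any time: (0.52 × 94 + 0.38 × 141)/235 = 43.6%.
- On therapy only: (0.52 × 94 + 0.34 × 141)/235 = 41.2%.

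Counting the trial at 41.2% (n = 80) and history at 43.6% (n = 235) gives a false-benefit rate of 5.8%. Section 2.1 does not state the ON grade for these figures, so they are a proxy.

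**The case against.** **The Section 10.8 entry can be read as a window.** The objective has two endpoints and the entry has two parts, so it most naturally means time on therapy for clinical ON and Reinduction II for MRI. That reading is fair but does not close the gap. If therapy means TOT17 therapy, the late patients will not have completed it when the analysis begins: Reinduction II is at about Continuation week 17, six months adds 26 weeks, and Section 5.2 still schedules an optional test at week 120. Nor does the table apply the window to TOT-XV/XVI.

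**Section 2.2 says most TOTXVI patients with symptomatic ON had symptoms before a stated timepoint.** That could be the Reinduction II MRI or the later TOT17 randomisation. If it is the MRI, at least half of events fall by month 9. For this reason the size above starts at f9 = 0.50. Evenly spread onset (37.5% by month 9) would give 12.6%, but conflicts with that reading and should not be the headline.

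**The analysis start is not a data cut.** Section 10.7 puts study completion at 3/2025, two years after primary completion. If all patients were followed to 24 months before the test, the bias in this model would vanish. The plan does not say so, and the size is conditional on this.

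**The historical counting window is not in the documents.** It may turn out to match, so the bias is possible rather than shown. The 2.5% benchmark also presumes cohorts exchangeable across treatment eras.

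**Stronger inferences that a reader might draw, and why they fail**
- *ON capture stops near month 10, giving 32% with 75% of events by month 9.* This applies the 4-week adverse-event limit to ON. Section 5.5 follows ON under TOT17, and Section 9.1 records Grade 2+ ON in a separate sentence. The reading is strained, though worth excluding explicitly.
- *The Section 10.7 dates imply 22 months of accrual and 27%.* At 60 per year that is 110 patients, about 55 per arm rather than 80; with 55 the figure is 20.8%. It also rests on evenly spread onset.
- *The plan has no place for dexamethasone duration.* Section 10.2 allows regression between randomised arms if factors are unbalanced. The covariate lacks a place only in the historical comparison.
- *The randomised comparisons are biased.* Short follow-up costs events in both arms and is not expected to favour either.

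**Conclusion.** The point stands for objective 1.2.2. As written, Section 10.5 permits a crude comparison between a partly short-followed trial arm and a historical cohort with no stated cut-off, and any error from longer historical counting runs in favour of intensive control. Under the stated assumptions the favourable false-positive rate is about 3-10% instead of 2.5% if 50-75% of events occur by month 9, and close to nominal, about 3%, if 90% do. The one gap taken from the documents' own figures gives about 6%. This is a modest distortion of a secondary, non-randomised comparison; it is not evidence that the trial's main conclusion is at risk. The radiographic half of 1.2.2 should not be called safe, because the historical MRI time point is not stated. A change is worth making before the data are examined.

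**What to change.** In Sections 10.5 and 10.8:

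1. Set one horizon from start of therapy for Grade 2+ ON and apply it to both arms and to TOT-XV/XVI.
2. For 1.2.2, compare cumulative incidence at that horizon, censoring at last assessment and treating death, relapse and transplant as competing events.
3. Restrict the historical cohort to patients meeting HYPERION eligibility, as the Section 10.4 chart review did.
4. Use the Reinduction II MRI in both cohorts for radiographic ON.
5. Give dexamethasone duration (Section 2.2) a place in the historical comparison, for example in a supportive regression.
6. Confirm that Grade 2+ ON capture under Sections 5.5 and 9.1 reaches the horizon.

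The cost is SAP wording and a modest extra analysis. The limit is follow-up. Activation on 08-28-2020 plus 36-42 months of accrual plus 24 months is about 8/2025 to 2/2026, after the 3/2025 completion date in Section 10.7. By 3/2025, about 55 months after activation, the last patient would have 55 − 42 = 13 to 55 − 36 = 19 months. Waiting for everyone to reach 24 months therefore does not fit the stated dates. The choices are censored estimation at the data cut, a shorter horizon that the follow-up supports, or revised dates.

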Brief Outline of Treatment Plan: Patients will be randomized on day 4 of induction therapy to either conventional or intensive blood pressure goals. Patients will be treated with the long-acting antihypertensive lisinopril to achieve blood pressure control as indicated by their randomized arm. Long-acting therapy will be adjusted every 3-4 days as needed to achieve targeted control based on the median of blood pressures obtained in that period. Treatment of hypertension to the target will continue until the completion of reinduction II therapy. Patients will be evaluated for osteonecrosis as indicated in their primary therapeutic protocol using MRI during reinduction II.
Study Design: Randomized unblinded trial of conventional vs. intensive hypertensive control. Evaluation of the MRIs defining the primary endpoint will be performed by a blinded radiologist.
Sample Size: We will randomize 160 evaluable patients (180 total).
Data Management: Data management and statistical analysis will be provided locally by the Comprehensive Cancer Center Hematological Malignancies Program and the Biostatistics Department at St. Jude Children’s Research Hospital.
Human Subjects: The risks to subject will be related to the toxicity of antihypertensive therapy. Side effects are anticipated to be mild and limited to reversible orthostatic/postural hypotension and transient increases in creatinine. Patients will be informed of this and other minor side effects during informed consent discussion. Adverse events will be monitored and reported and treated appropriately.

TABLE OF CONTENTS

1.0	OBJECTIVES	1
1.1	Primary Objective	1
1.2	Secondary Objectives	1
1.3	Exploratory Objectives	1
2.0	BACKGROUND AND RATIONALE	2
2.1	Background	2
2.2	Rationale	2
2.3	Background and Rationale for Ancillary and Exploratory Studies	3
3.0	RESEARCH PARTICIPANT ELIGIBILITY CRITERIA AND ENROLLMENT	4
3.1	Inclusion Criteria	4
3.2	Exclusion Criteria	4
3.3	Research Participant Recruitment and Screening	5
3.4	Enrollment on Study at St. Jude	5
3.5	Enrollment Instructions for Collaborating Sites	5
4.0	TREATMENT PLAN	6
4.1	Treatment	6
4.2	Participation of St. Jude Affiliates in the Treatment Plan	9
4.3	Treatment Modifications for Collaborating Sites	9
4.4	Supportive Care	9
4.5	Symptom Survey and Semi-structured Interviews	10
5.0	REQUIRED EVALUATIONS, TESTS, AND OBSERVATIONS	12
5.1	Pre-Study Evaluations	12
5.2	Evaluations during Therapy	12
5.3	Response Evaluations	13
5.4	Off-Study Evaluations	13

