4.0 TREATMENT PLAN

4.1 Treatment

Following enrollment and randomization, a target systolic blood pressure range will be chosen for each participant based on their randomization arm, age, sex, and height. Target blood pressures for girls randomized to standard and intensive blood pressure control are shown in Tables 1a and 1b, respectively. Target blood pressures for boys randomized to standard and intensive blood pressure control are shown in Tables 2a and 2b, respectively. For patients ages 10-12 years, select the height column closest to their true height. If two columns are equidistant from their true height, select the lower height.

Patient randomization will be stratified based on patient’s location (Memphis vs. other), use of antihypertensives prior to randomization, and factors known to influence osteonecrosis risk, specifically sex and self-declared race (non-Hispanic white vs. other).

Patients will begin antihypertensive therapy to achieve the targeted blood pressure on day 4. Patients already receiving antihypertensive therapy prior to day 4 should have their therapy adjusted according to the guidelines below. **Patients requiring an antihypertensive should be started on lisinopril** (initial dose 2.5mg daily) unless there is a contraindication to its use. Lisinopril dose may be escalated as indicated. Recommended second line agents for use when lisinopril is contraindicated include angiotensin receptor blockers (e.g. losartan 25mg daily), beta-blockers (e.g. carvedilol 3.125mg BID or, if cardiac rate control is required, metoprolol 12.5mg BID) or a calcium channel blocker (e.g. amlodipine 2.5mg daily).

Table 1a: Girls’ Standard Arm Systolic Blood Pressure Targets							
Age/Height (cm)	Height 5%	Height 10%	Height 25%	Height 50%	Height 75%	Height 90%	Height 95%
10 years	130 cm	132 cm	136 cm	141 cm	146 cm	150 cm	153 cm
Standard Low End Target (mmHg)	109	110	111	112	113	115	116
Standard High End Target (mmHg)	113	114	114	116	117	119	120
11 years	136 cm	138 cm	143 cm	148 cm	153 cm	157 cm	160 cm
Standard Low End Target (mmHg)	111	112	113	114	116	118	120
Standard High End Target (mmHg)	115	116	117	118	120	123	124
12 years	143 cm	146 cm	150 cm	155 cm	160 cm	164 cm	166 cm
Standard Low End Target (mmHg)	114	115	116	118	120	122	122
Standard High End Target (mmHg)	118	119	120	122	124	125	126
13+ years	All heights						
Standard Low End Target (mmHg)	130						

Standard High End Target (mmHg)	135						

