Intensive Low End Target (mmHg)	110						
Intensive High End Target (mmHg)	120						

Patients will begin antihypertensive therapy to achieve the targeted blood pressure on Day 4 of Remission Induction on TOT17. Patients already receiving antihypertensive therapy prior to Day 4 should have their therapy adjusted according to the guidelines below.

During outpatient visits, blood pressures measured should be performed after the patient has been sitting at rest for at least 10 minutes and is not experiencing pain or anxiety.

During induction, blood pressure adjustments will be made for each patient based on the mean blood pressure over the preceding 4 days (minimum 2 measurements) unless indication for immediate change is met (listed below). Blood pressures obtained while a patient is sedated for procedures should not be included in the evaluated blood pressures when determining whether to adjust antihypertensive medications. Patients with mean blood pressures outside of the target range should have antihypertensive therapy adjusted in an attempt to reach the goal range. However, if prior changes to medication have been made within 7 days and blood pressures are both 1) closer to the target range than at the time of prior medication change and 2) within 10mmHg of the goal range following that change, further modifications can be delayed until a subsequent visit.

Immediate changes to antihypertensive therapy are indicated if:

- 1) systolic pressures are more than 15mmHg above the high end target,
- 2) patients are experiencing headache, vision changes, or neurologic symptoms attributable to hypertension,
- 3) the patient has experienced an episode of syncope,
- 4) the patient's systolic pressure is below 90, or
- 5) the patient is experiencing unacceptable toxicity from their current antihypertensive therapy.

Patients will continue antihypertensive therapy (as needed to achieve the targeted blood pressure range) during phases of therapy with scheduled glucocorticoids (i.e. Induction and Continuation, including Reinduction 1 & 2). Patients should continue antihypertensive therapy during other phases if tolerated. Caution is warranted in consolidation (due to the risk of altered renal perfusion or kidney injury) and during immunotherapy (due to the risk of cytokine release induced hypotension).

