5.0 REQUIRED EVALUATIONS, TESTS, AND OBSERVATIONS

5.1 Pre-Study Evaluations

All entry/eligibility studies must be performed within 10 days prior to entry onto the trial (unless otherwise specified). Evaluations performed as part of TOT17 evaluation and therapy should be used when feasible to avoid duplicate studies.

Evaluation— must be obtained before enrollment	Within 10 days prior to enrollment
History and physical exam with height (cm), weight (kg), and BSA	X
Diagnosis of acute lymphoblastic leukemia/ lymphoma (ALL)	X
Laboratory studies: CBC with Diff, Chem 18, Urinalysis, PT, PTT	X
Echocardiogram	X
Pregnancy test for females of childbearing potential	X

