5.2 Evaluations during Therapy

Evaluation	Timing during Induction	Timing post-Induction
Ambulatory blood pressure monitoring (ABPM)	Once for 12-30 hours on day 4-7, once for 12-30 hours on day 23-28	-
Magnetic resonance imaging of hip and knee	Once during Days 23-28#	Reinduction 2 per Total 17 protocol
Vasomotor testing (arterial elasticity, pulse wave velocity) #	Once during Days 23-28	Once between Early Intensification day 57 and Consolidation day 28, (optional) once Continuation week 120 ±2 weeks
Serum for vascular biomarkers ^{&}	Day 22 +/- 2 days	Week 17 of Continuation (Reinduction II)
Echocardiogram		Once during week 17-19 of Continuation (Reinduction II)#
Symptom survey (PROMIS: Ped 25 Profile, Pain interference 8a, Physical activity 8a, Mobility 8a)	Once on day 23-28	Week 17 of Continuation (Reinduction II) ± 2 weeks, week 49 ± 3 weeks
Semi-structured interview of treatment and symptom burden #		Week 49 ± 3 weeks (with symptom survey)

All days/ weeks refer to the date of Total 17 therapy (i.e. day 22 refers to day 22 of Total 17, not the 22nd day since HYPERION entry or randomization).

***The St. Jude IRB requires that a female patient of childbearing potential must have a negative pregnancy test as a condition of clinical research eligibility.*

SJCRH Memphis patients only

& See HYPERION Manual of Operations for collection, processing and shipping instructions.

Obtain other studies as needed for good patient care and per the TOT17 protocol.

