6.0 EVALUATION CRITERIA

6.1 Response Criteria

All patients will be evaluated clinically and radiographically for the development of osteonecrosis. Patients with radiographic (MRI or plain film x-ray) findings of osteonecrosis will be assessed for symptoms by the treating physician or designee. CTCAE version 4 criteria will be used to categorize the severity of osteonecrosis. MRI imaging will be centrally reviewed by a radiologist blinded to treatment assignment to assess the involvement of epiphyseal surfaces (0, <30%, ≥30%) which will be determined for each effected joint.

Blood pressures for each patient will be documented in the research database as the median of each week during induction and the median of each post-induction phase.

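### The achieved-blood-pressure model lists no phase or arm-by-phase term and leaves out two stratification factors, so it cannot show whether the arms separated in the steroid phases

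*Combined protocol and SAP*

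**What the plan says.** Objective 1.2.3 compares the pressures achieved in the two arms, from routine care and from ambulatory monitoring. Section 10.5 does this by regression "using mixed effect models to account for intra-patient repeated blood pressure measurements", where "the explanatory variables include the BP control arm (intensive vs. conventional), age, sex, race and a random effect with AR(1) working covariance structure". Section 10.2 stratifies randomisation by site, gender, race/ancestry and hypertension requiring more than one dose of medication before Day 4, and says that secondary analyses will not be stratified.

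The data for this model are as follows.

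- Routine pressures (Section 6.1) are stored as "the median of each week during induction and the median of each post-induction phase".
- Ambulatory monitoring (Section 5.2) is done "Once for 12-30 hours on day 4-7, once for 12-30 hours on day 23-28".
- Randomisation: "Patients will be randomized on day 4 of induction therapy" (Protocol Summary). Treatment: "Patients will begin antihypertensive therapy to achieve the targeted blood pressure on day 4" (Section 4.1).
- Pre-study evaluations (Section 5.1) list "History and physical exam with height (cm), weight (kg), and BSA" and name no blood pressure.

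Section 2.2 gives induction and reinduction the critical role in osteonecrosis. Section 4.1 keeps treatment to target during phases with scheduled glucocorticoids and continues it elsewhere only if tolerated, with caution in consolidation and immunotherapy.

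**The concern.** By the protocol's own logic, the arm difference should vary over time: pressure is driven to target in the steroid phases and control is relaxed elsewhere. A model with a single arm coefficient averages over this. If the primary comparison shows no effect, the reader must know whether the arms failed to separate when it mattered or separated without benefit. This is the only planned between-arm test of achieved pressure, and as listed it cannot answer that.

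Three smaller matters bear on the same model. Sex and race are in it, but site and the pre-Day-4 hypertension stratum are not, although both are recorded for every patient at randomisation and the second carries information on early pressure. The text does not say how AR(1) handles gaps of one week in induction and of whole phases later. And the week 1 median would enter as an outcome although part of it precedes randomisation.

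**Working it through.** **The plan's own figures.** Section 10.5 gives no SD, target difference or power for blood pressure. The only stated power is 78.7% for the primary endpoint. It reproduces: the control rate is 0.854 × 50/120 + 0.146 × 0.20 = 0.385, and the exact one-sided test of 0.385 against 0.20 with 80 per arm has power 78.66%. That calculation does not involve this model.

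**1. What one averaged coefficient can and cannot show.** With complete data and AR(1) by record order, with or without a patient intercept, the first and last of n records each get weight 1/[2 + (n−2)(1−r)], and each record between gets (1−r) times that. Assume 10 records, of which 5 are weekly induction medians. Induction then gets [1 + 4(1−r)]/[2 + 8(1−r)] = 0.50 for any r. Three hypothetical patterns give the same coefficient:

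| Difference in induction | Difference later | Model coefficient |
|---|---|---|
| 5 mmHg | 5 mmHg | 5 mmHg |
| 10 mmHg | 0 | 5 mmHg |
| 0 | 10 mmHg | 5 mmHg |

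Only an arm-by-phase term tells them apart.

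**2. The week 1 record.** Counting days from the start of TOT17, as Section 5.2 does, week 1 holds Days 1–3 before randomisation and Days 4–7 from it. With 10 records the first has weight:

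- r = 0.3: 1/(2 + 8 × 0.7) = 1/7.6 = 13%
- r = 0.6: 1/(2 + 8 × 0.4) = 1/5.2 = 19%
- r = 0.8: 1/(2 + 8 × 0.2) = 1/3.6 = 28%

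If that record showed no arm difference and all others a constant one, the coefficient would be 87%, 81% or 72% of the later difference. This is the outer limit, since some separation may occur on Days 4–7.

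**3. Unequal spacing.** For a working covariance W and true covariance S, the weights are w = W⁻¹1/(1′W⁻¹1), and the variance of the arm contrast is (2/80)·w′Sw, against an optimum of (2/80)/(1′S⁻¹1). Assumptions, none of them in the documents: total variance 100 (SD 10 mmHg); 4 to 6 weekly medians plus 3 or 4 phase medians over about 9 months; correlation of the serial component 0.70 to 0.95 per week; complete data; constant arm effect; AR(1) parameters at their best-fitting values. With a patient intercept in the model:

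- Smallest loss (variance 50 between patients, 40 serial, 10 residual; 0.90 per week; 4 + 4 records): optimum SE 1.296, order-based 1.296 × 1.012 = 1.312 mmHg.
- Largest loss (0, 90, 10; 0.80 per week; 6 + 4 records): optimum SE 0.766, order-based 0.766 × 1.122 = 0.859 mmHg; variance ratio 1.122² = 1.26.

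So the SE rises by 1.2% to 12.2%, and the model-based SE is about right. Without a separate patient intercept, the model-based SE is 0.77 to 1.02 of the true SE, so intervals could be too narrow. Section 10.5 does not settle which model is meant. Leaving out a time profile common to both arms changes the true SE of the overall contrast by under 1%.

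**4. A baseline covariate.** Adjustment multiplies the variance by 1 − ρ². For assumed ρ of 0.2, 0.4, 0.5 and 0.6 this is 0.96, 0.84, 0.75 and 0.64, a reduction of 4% to 36%. With SD 10 and one value per patient, SE = 10 × √(2/80) = 1.58 mmHg, falling to 1.55 at ρ = 0.2 and 1.26 at ρ = 0.6.

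**5. Is precision limiting?** For ages 13 and over the targets are 110–120 and 130–135 mmHg, with midpoints 115 and 132.5, a gap of 17.5. At SD 10 and 80 per arm, two-sided 5% power is 88.5% for 5 mmHg and over 99% for 8 mmHg, before any baseline gain.

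**The case against.** The best defence has several parts.

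- *The covariate list is worded as open, and Section 10.2 allows regression models if important factors are unbalanced.* True, but an open list does not prespecify phase or arm-by-phase terms. The imbalance clause is also unlikely to bring in site or the hypertension stratum, because stratified randomisation is meant to balance them.
- *Other evidence on separation exists.* Section 6.3 defines a per-protocol set by 80% of time in range, Section 10.3 monitors target attainment, and the stored medians allow description by phase. This softens the point. But the 80% rule classifies patients over the whole period, the monitoring covers the intensive arm only, and no phase-specific comparison of arms is planned.
- *Indexing AR(1) by order is inferred, as is use of the stored medians as the response.* This stands. The plan is silent on both, so the spacing issue is a gap to close rather than a demonstrated error. It does not touch ambulatory monitoring if each of the two sessions gives one summary.
- *Precision is adequate.* This largely stands, as step 5 shows.

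A reader might infer that the plan discards a baseline pressure it already holds. The documents do not support that. No numeric pre-randomisation pressure is defined as study data: the first ambulatory session falls on Days 4–7, when treatment has begun, and the week 1 median is mixed. Routine readings before Day 4 should exist in the chart, since titration uses the preceding 4 days, but they would have to be extracted. Some patients will already be on antihypertensives, and titration to target may keep ρ low. Nor does omitting time cost precision; its cost lies in what is estimated.

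**Conclusion.** The point holds as one of interpretability. As listed, the model returns a single average arm difference and cannot show separation in induction and reinduction, which follows from the listed terms without any numerical assumption. Two recorded stratification factors are left out for no stated reason. The week 1 record needs a rule. The precision effects are modest and conditional: about 1% to 12% in SE if AR(1) is indexed by order, and a 4% to 36% variance reduction if a pre-Day-4 mean can be obtained. Both ranges rest on assumed correlations, and the first also on assumed phase timings, which the documents do not give. It would go too far to say that the trial's main conclusion is at risk: this is a secondary objective, and the primary test and sample size do not use this model. The change is still worth making because it costs little and bears on how a null primary result would be read.

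**What to change.** In Section 10.5, specify the model for routine systolic pressure as follows.

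- Fixed effects: arm, phase, arm-by-phase, age, sex, race, site and the pre-Day-4 hypertension stratum as recorded at randomisation.
- Report the arm difference with its interval separately for the glucocorticoid phases. Section 4.1 counts both reinductions within Continuation, so list the phases and give each reinduction its own median.
- Use an elapsed-time (spatial power) covariance, state whether there is also a patient intercept, and use robust standard errors. An unstructured matrix is less attractive: 10 occasions would need 10 × 11/2 = 55 parameters.
- Keep readings from before Day 4 out of the outcome series, for example by starting the week 1 median after randomisation.
- Model the two ambulatory sessions separately.
- Where routine systolic readings before Day 4 can be extracted, add their mean as a covariate, with a stated rule for patients who have none.

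The cost is SAP wording and a small chart extraction. Neither the sample size nor the primary analysis changes.
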